3.2 Design type

This trial adopts a prospective, randomized, multicenter, open-label and parallel-arm clinical research method. The whole observation period is 1 year for this trial. See P12 “Clinical trial flow chart” for details.

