8.1 Definition of adverse events

Adverse event (AE) refers to the adverse medical conditions or deterioration of the original medical condition after or during drug treatment, regardless of whether there is a causal relationship with the drug. Adverse medical conditions can be symptoms (such as nausea, and chest pain), signs (such as tachycardia, and hepatomegaly), or abnormal examination results (such

as laboratory examination, and ECG). In clinical researches, AE can occur at any time, including the adverse medical conditions in the screening period, even if no study treatment is received.

The term AE includes severe ones and non-severe ones.

8.1.1 Concerned adverse reactions of test drug FK506:

Adverse reactions associated with immunosuppressive drugs are often difficult to be determined due to the underlying diseases of patients and combined use of multiple drugs at the same time. The following adverse reactions are reversible, or can be reduced or eliminated after dose reduction. Compared with intravenous administration, oral administration has a lower incidence of adverse reactions.

Cardiac abnormalities

Common: Ischemic coronary artery disease, and tachycardia; Unusual: Ventricular arrhythmia and cardiac arrest, heart failure, cardiomyopathy, ventricular hypertrophy, supraventricular arrhythmia, palpitation, abnormal ECG, abnormal heart rate and pulse; Rare: Pericardial effusion; Very rare: Abnormal echocardiography.

Blood and lymphatic system abnormalities

Common: Anemia, leucopenia, thrombocytopenia, leucocytosis and abnormal erythrocyte analysis; Unusual: Abnormal coagulation function, pancytopenia, and neutropenia; Rare: Thrombotic thrombocytopenic purpura, and low prothrombin; Unknown: Pure red cell aplasia, agranulocytosis, and hemolytic anemia.

Neurologic abnormalities

Very common: Tremor, and headache; Common: Epilepsy, disturbance of consciousness, paresthesia and dullness, peripheral neuropathy, vertigo, dysgraphia and nervous system disorders; Unusual: Coma, central nervous system hemorrhage and cerebrovascular accident, paralysis and local anesthesia, encephalopathy, abnormal language function and cognitive impairment; Rare: Hypertonia; Very rare: Myasthenia.

Eye and ear abnormalities

Common: Blurred vision, photophobia, and eye discomfort; Unusual: Cataract; Rare: blindness, abnormal ear and labyrinth; Common: Tinnitus; Unusual: Hearing retardation; Rare: Neurogenic deafness; Very rare: Hearing loss.

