8.3 Records of adverse events

The information of AEs to be collected in this research includes the following aspects:

- Endpoint event
- Adverse events related to the test drugs (according to the judgment of the investigators)
- Serious adverse event

Cycle of adverse event collection

The collection of AEs and adverse drug reactions (DAEs) of concern will be carried out throughout this research, from randomization to site close-out visit (SCV, included).

SAE records will be carried out throughout this research, from the time of signing the Informed Consent Form to SCV (included).

Follow-up of unresolved adverse events

If any AE, DAE and SAE of concern remain unresolved at the patient's last study visit, the investigators shall follow up these events in accordance with the medical instructions as required for medical needs in this research, but it is not necessary to record further in the electronic case report form (eCRF). If deemed necessary, the Sponsor reserves the right to obtain the additional information on unresolved AE/SAE of concern.

Variables

For each non-serious AE and DAE of concern, the following variables will be collected:

- AE (verbatim record);
- AE start and end dates;
- Maximum intensity;

- Whether the AE is serious;
- The investigators' assessment of the causal relationship with the test drug (yes or no);
- Measures and outcomes taken for the test drug

In addition, the following variables will be collected for SAE:

- Date when AE meets SAE criteria;
- Date when the investigators find SAE;
- Reasons for classifying AE as SAE;
- Date of admission;
- Date of discharge;
- Possible causes of death
- Date of death;
- Autopsy performed (if any);
- Autopsy results
- AE description
- Assessment of causality with this research procedure;
- Assessment of causality with the other drugs

It is important to distinguish serious AE from severe AE. Severity is the index of intensity evaluation, while seriousness is defined according to the criteria in Section 8.2. AE with severe intensity is not necessarily serious. For example, nausea for several hours may be considered as severe nausea, but not SAE. On the other hand, a stroke that results in only a limited degree of disability may be considered as a mild stroke, but should be considered as SAE.

The definition of intensity classification is as follows:

1. Mild (signs or symptoms are felt but easily tolerated)

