2. Moderate (the degree of discomfort is enough to interfere with normal activities)
3. Severe (resulting in disability and inability to perform normal activities)

Collection of causalities

The investigators will assess the causalities between the test drugs and each case of AE, and answer the following questions with "Absolutely related, Probably related, Possibly related, Possibly unrelated, and Unrelated".

"Do you think there is a reasonable possibility that the event is caused by the test drug?"

For SAE, the causalities between the event and other drugs and research procedures also need to be evaluated. Note: for SAE related to any research procedure, causality should be "possibly related".

Adverse events based on signs and symptoms

All concerned AEs (see sections 8.1.1 and 8.1.2), including those spontaneously reported by the patients, those reported in response to the open-ended question by the investigators, "Have you

had any health problems since the last visit/inquiry?", or those found through observation will be all collected and recorded in eCRF. In the collection of AE information, the list of signs and symptoms shall be preferred as the record of diagnosis (if possible). However, if the diagnosis is known and there are other signs or symptoms not usually present in the diagnosis, the diagnosis and each other sign or symptom shall be recorded separately.

Adverse events based on examination and inspection

During this research, the laboratory safety assessment will not be carried out routinely (except at baseline), but can be carried out at the discretion of the investigators. When an AE, DAE, SAE or potential endpoint of concern is involved, different assessments may be required, including local laboratory assessment, and appropriate collection is needed before entry into eCRF.

The examination results of vital signs mandated by the Protocol shall be summarized in the clinical study report (CSR). Therefore, when the laboratory test values and protocol-mandated vital signs evaluation by the investigators show that the results are worse than the baseline level and meet the AE criteria or when they act as are the reasons for discontinuing the test drug treatment, such situations will be reported as AE.

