8.1.6. Safety analysis

Safety analysis mainly adopts safety set. All adverse events are coded by MedDRA 20.0 to describe the total number and incidence of adverse events (including serious adverse events), and the

frequency table is used to describe the frequency, severity of each adverse event and its relationship with the treatment. Adverse events relevant (related, probably related, and possibly related) to this research treatment are described and listed separately. Other safety indicators will also be described and summarized. The laboratory changes with clinical significance will be counted as AE.

9. Statistical analysis results

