9.5. Safety analysis (SS)

9.5.1. Adverse event (AE)

Table 62. Between-group comparison of AE

Items	Experimental group			Control group			P-value
	No. of AEs	No. of subjects	Percentage	No. of AEs	No. of subjects	Percentage	
AE							
AE of severe severity							
Drug-related AE							
Serious adverse event (SAE)							
Drug-related SAE							
Drop-out due to AE							
Drop-out due to SAE							

Note 1: The definitions related to drugs are “definitely related”, “probably related”, “possibly related”, “unlikely related” and “not related”.

Note 2: The data of SAE that cause the drop-out came from the external file “XX”.

Table 63. characteristics of AE in each group

Items	Experimental group			Control group			P-value
	No. of AEs	No. of subjects	Incidence	No. of AEs	No. of subjects	Incidence	
Relationship with study drug							
Definitely related							
Probably related							

Items	Experimental group			Control group			P-value
	No. of AEs	No. of subjects	Incidence	No. of AEs	No. of subjects	Incidence	
Possibly related							
Unlikely related							
Not related							
Outcome	Recovered/resolved						
	Recovered/resolved with sequelae						
	Not recovered						
	Recovering/resolving						
	Death						
	Unknown						

Table 64. Between-group comparison of SAE

Items	Experimental group (n=XX)			Control group (n=XX)			Total (n=XX)	P-value
	No. of AEs	No. of subjects	Incidence (%)	No. of AEs	No. of subjects	Incidence (%)		
Results in death								
Requires hospitalization								
Prolongs hospitalization								
Disability								
Dysfunction								
Congenital malformation								
Life threatening								
Other								

Table 65. Summary of AE base on SOC and PT coding

Indicator	Experimental group (n=XX)			Control group (n=XX)			Total (n=XX)	P-value
	No. of AEs	No. of subjects	Incidence (%)	No. of AEs	No. of subjects	Incidence (%)		
AE								

Indicator	Experimental group (n=XX)			Control group (n=XX)			Total (n=XX)			P-value
	No. of AEs	No. of subjects	Incidence (%)	No. of AEs	No. of subjects	Incidence (%)	No. of AEs	No. of subjects	Incidence (%)	
SOC1										
PT1										
PT2										
...										
SOC2										
PT1										
PT2										
...										

Table 66. Summary of adverse reactions base on SOC and PT coding

Indicator	Experimental group (n=XX)			Control group (n=XX)			Total (n=XX)			P-value
	No. of AEs	No. of subjects	Incidence (%)	No. of AEs	No. of subjects	Incidence (%)	No. of AEs	No. of subjects	Incidence (%)	
Adverse event										

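### Protocol 8.3 is inconsistent on which adverse events are collected and never requires all of them, yet the SAP compares all adverse events between arms with P-values

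*Protocol*

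**What the plan says.** The protocol and SAP set the scope of AE collection in several ways.

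- **Definition.** Protocol 8.1 defines an AE "regardless of whether there is a causal relationship with the drug".
- **Collection list.** Protocol 8.3 opens with "The information of AEs to be collected in this research includes the following aspects" and gives three items: endpoint events, "Adverse events related to the test drugs (according to the judgment of the investigators"), and serious AEs. Non-serious AEs judged unrelated have no item.
- **Collection period.** The same section says "The collection of AEs and adverse drug reactions (DAEs) of concern will be carried out throughout this research", from randomisation to close-out.
- **Signs and symptoms.** Further on, 8.3 requires eCRF entry for "All concerned AEs (see sections 8.1.1 and 8.1.2), including those spontaneously reported by the patients", as well as those elicited by an open question or found by observation.
- **Causality.** 8.3 records causality as yes or no for each non-serious AE of concern. It also asks for a five-level grade for each AE, and two of those levels are on the unrelated side.
- **Analysis.** SAP 8.1.6, like Protocol 11.3.6, states: "All adverse events are coded by MedDRA 20.0 to describe the total number and incidence of adverse events". "Table 62. Between-group comparison of AE" has one row for AEs and another for drug-related AEs, with a P-value column. Table 63 has rows for events unlikely to be related and not related. Table 65 gives P-values by system organ class and preferred term.

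Protocol 3.2 describes the trial as a "prospective, randomized, multicenter, open-label and parallel-arm clinical research method".

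**The concern.** An all-AE comparison needs the same complete capture in both arms. If causality or membership of a list decides whether an event is entered, the table counts what the investigator chose to record. In an open-label trial the investigator knows the drug when making that choice. The two drugs have different known reactions, so attribution could plausibly differ by arm and could create or hide a difference in AE incidence.

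Safety is in the title and the objective, which looks for a safer as well as a more effective choice. SAP 4.1 reports 12 sites. With more than one collection rule in the protocol, sites could apply different ones.

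**Working it through.** There is no planned figure to reproduce, because neither document states an AE rate. The check first compares the texts, then illustrates the size.

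**Step 1. Three scopes side by side**

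| Scope | Where it stands |
|---|---|
| Drug-related AEs, serious AEs and endpoint events | Protocol 8.3, opening list |
| AEs of concern (8.1.1 and 8.1.2) | Protocol 8.3, collection period, variables, and signs and symptoms |
| All AEs | Protocol 8.1 (definition), 8.3 (five-level causality scale), 11.3.6; SAP 8.1.6 and Tables 62, 63, 65 |

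The first scope omits non-serious AEs judged unrelated. The second is wider but stops at the listed reactions. The third is what the analysis needs. Laboratory and vital-sign worsening (8.3) and serious AEs (8.4) are reported with no causality filter, but each rule covers only its own kind of event. No sentence in 8.3 tells a site to record every non-serious AE.

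**Step 2. Illustration if only events judged related were entered**

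Inputs:
- 135 children per arm (Protocol 3.3.2, SAP 4.2.2).
- Assumed: true incidence p = 60% in both arms. Share of events judged related: a = 70% in one arm and 50% in the other. Each affected child has k AEs, attributed independently.

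A child is counted if at least one event is recorded, so the recorded incidence is r = p × [1 − (1 − a)^k]. The chance of P<0.05 uses the two-sided normal approximation for two proportions at 5%.

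| k | r at a = 70% | r at a = 50% | False gap (points) | Chance of P<0.05 |
|---|---|---|---|---|
| 1 | 0.60 × 0.70 = 42.0% | 0.60 × 0.50 = 30.0% | 12.0 | about 54% |
| 2 | 0.60 × 0.91 = 54.6% | 0.60 × 0.75 = 45.0% | 9.6 | about 35% |
| 3 | 0.60 × 0.973 = 58.4% | 0.60 × 0.875 = 52.5% | 5.9 | about 16% |
| 4 | 0.60 × 0.9919 = 59.5% | 0.60 × 0.9375 = 56.3% | 3.3 | about 8% |

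For k = 1, the standard error under no difference, with pooled proportion 0.36, is √(2 × 0.36 × 0.64 / 135) = 0.0584. Under the recorded rates it is √[(0.42 × 0.58 + 0.30 × 0.70) / 135] = 0.0580. Then (0.12 − 1.96 × 0.0584) / 0.0580 = 0.095, and Φ(0.095) ≈ 0.54.

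**Step 3. Sensitivity, with k = 1**

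- Attribution 60% v 50%, p = 60%: recorded 36% v 30%, chance about 18%.
- Attribution 70% v 40%, p = 60%: recorded 42% v 24%, chance about 89%.
- Attribution 70% v 50%: chance about 34% at p = 40% and about 75% at p = 80%.
- Equal attribution: no expected gap, and the error rate stays near 5%.

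The model leaves out serious AEs and laboratory or vital-sign AEs, which are entered whatever their cause.

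**The case against.** A reader might infer that the protocol collects only drug-related AEs and that the between-arm comparison is therefore biased. The documents do not support that.

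- The list in 8.3 is introduced as what the information includes. It does not say only.
- A yes/no causality variable, and a five-level scale with an unrelated grade, would serve little purpose if unrelated events were never entered. Protocol 11.3.6 codes all AEs and lists the treatment-related ones separately, so the protocol itself expects unrelated events in the data.
- It would also be wrong to expect the unrelated rows of Table 63 to be nearly empty. Unrelated serious AEs, unrelated AEs of concern and laboratory or vital-sign AEs would all enter them.
- The tacrolimus list in 8.1.1 is much longer than the mycophenolate list in 8.1.2, which suggests a different symptom list per arm. However, 8.3 cites both sections together and does not assign one to each arm. If the combined list applies to every child, the unequal lengths create no arm-specific filter.
- The 54% figure assumes one AE per affected child. Follow-up lasts a year with eight AE reviews, and more events per child shrink the gap quickly.

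These points stand, and they limit the claim. They do not remove the inconsistency. The causality scales say how to grade an event that has been entered, not which events to enter. The wider rule still stops at AEs of concern, and the protocol does not say whether that means one combined list or one per drug.

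**Conclusion.** The protocol gives at least two incompatible collection rules, and the analysis assumes a third. A site that followed the stated scope of 8.3 could omit non-serious AEs that Tables 62, 63 and 65 count. The all-AE comparison would then be incomplete and open to arm-dependent attribution.

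Bias needs two further conditions: sites applied the restrictive wording, and attribution differed by arm. Neither is shown. At the assumed 60% incidence and 70% v 50% attribution, the chance of a false P<0.05 runs from about 54% down to about 8% as AEs per affected child go from one to four. Incidence, attribution and AE count are all assumptions, so these figures show only that the effect could range from large to slight. The point is worth correcting because the correction is cheap.

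**What to change.** In Protocol 8.3, replace the three-item list and the limit to AEs of concern with one rule: every AE is recorded in both arms from randomisation, regardless of causality or of membership of the lists in 8.1.1 and 8.1.2. Keep causality as a recorded attribute, so that drug-related AEs can still be tabulated separately. Keep the existing collection of serious AEs from consent.

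The cost is one amended passage and some extra eCRF entries. The open question is already in 8.3 and makes no distinction by arm, and the flow chart already reviews AEs at visits 2 to 9.

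If collection is over, establish which rule each site applied. Where it was not all AEs, relabel Tables 62, 63 and 65 to match what was collected, and draw no conclusion on overall AE incidence.

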Like other potent immunosuppressants, tacrolimus administration shows an increased risk of infection (viruses, bacteria, fungi and protozoa). Existing infections may be aggravated, and the systemic and local infections may occur. Patients treated with immunosuppressants, including tacrolimus, have been reported to have BK virus-related nephropathy and JC virus-related progressive multifocal leukoencephalopathy (PML).

Injury, intoxication and operation complications

Benign, malignant and unclear tumors (including cysts and polyps). Patients treated with immunosuppressants have an increased risk of malignant tumors. Benign and malignant tumors,

including EBV-related lymphoid hyperplasia and skin malignancies, have been reported to have possible association with the tacrolimus treatment.

Vascular abnormalities

Very common: Hypertension; Common: Bleeding, thrombus and local ischemia, peripheral vascular abnormalities, and hypotension; Unusual: infarction, limb deep vein thrombosis, and shock.

General abnormalities and administration site symptoms

Common: Weakness, fever, edema, pain and discomfort, elevated blood alkaline phosphatase, weight gain, and body temperature sensation disorder; Unusual: Multiple-organ failure, influenza like symptoms, temperature intolerance, chest compression, tension, paresthesia, elevated blood lactate dehydrogenase and weight loss; Rare: Thirst, fall, reduced activity, and ulcer; Very rare: Increased adipose tissue; Unknown: Death or sudden cardiac death, and abnormal gait.

Immune system abnormalities and hepatobiliary abnormalities

Allergic and anaphylactic reactions are observed in patients treated with tacrolimus.

Common: Abnormal liver function, cholestasis and jaundice, hepatocyte injury, hepatitis and cholangitis; Rare: Hepatic artery thrombosis, and venous occlusive liver disease; Very rare: Liver failure, and biliary stricture;

Reproductive system and breast abnormalities

Unusual: Dysmenorrhea and uterine bleeding; Unknown: Benign prostatic hyperplasia, and mental disorders; Very common: Insomnia; Common: Anxiety, confusion and disorientation, despondency, depression, emotional instability and disorder, nightmares, hallucinations and mental disorders; Unusual: Mental abnormality; Unknown: Aggressive behavior, and agitation.

8.1.2 Concerned adverse reactions of test drug MMF:

Infection

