If the deterioration of laboratory test values/vital signs is related to clinical signs and symptoms, the signs and symptoms will be reported as AE and relevant laboratory results/vital signs will be used as supplementary information. Investigators shall use clinical terms rather than laboratory terms (e.g. renal failure rather than elevated creatinine) as much as possible in the report. If no clinical signs or symptoms are present, the clinically relevant deterioration of non-mandatory parameters shall be reported as AE and SAE.

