11.3.6 Safety analysis

Safety analysis mainly adopts safety set. All adverse events are coded by MedDRA 20.0 to describe the total number and incidence of adverse events (including serious adverse events), and the frequency table is used to describe the frequency, severity of each adverse event and its relationship with the treatment. Adverse events relevant (related, probably related, and possibly related) to this research treatment are described and listed separately. Other safety indicators will also be described and summarized. The laboratory changes with clinical significance will be counted as AE.

12. Ethical principles

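### Protocol 8.3 read literally prefers a symptom list to the diagnosis and conflicts with its own next sentence, so infections can be split across organ classes in SAP Tables 65 and 66

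*Protocol*

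**What the plan says.** Under its heading on AEs based on signs and symptoms, Protocol 8.3 states that "the list of signs and symptoms shall be preferred as the record of diagnosis (if possible". An exception follows: "if the diagnosis is known and there are other signs or symptoms not usually present in the diagnosis", then "the diagnosis and each other sign or symptom shall be recorded separately". Under the heading on examination findings, the same section adds: "Investigators shall use clinical terms rather than laboratory terms (e.g. renal failure rather than elevated creatinine". It also says that when a laboratory deterioration comes with clinical signs and symptoms, these are the AE and the laboratory result is supplementary.

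Infection is a named risk of both drugs. Protocol 8.1.1 says that "tacrolimus administration shows an increased risk of infection (viruses, bacteria, fungi and protozoa". Protocol 8.1.2 has its own infection entry for MMF and names infection and sepsis among the events more common in children. In the 8.1.1 lists, cough and dyspnea stand under respiratory, diarrhea under gastrointestinal, and fever under general abnormalities.

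Protocol 11.3.6 and SAP 8.1.6 code AEs in MedDRA 20.0 and state: "The laboratory changes with clinical significance will be counted as AE". SAP 9.5.1 then compares the arms. Table 65, titled "Summary of AE base on SOC and PT coding", gives number of AEs, number of subjects, incidence and a P-value for each class and term. Table 66 does the same for adverse reactions. Neither document has a rule for regrouping symptom records into one diagnosed episode.

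**The concern.** The unit of recording decides what the organ-class tables can show. If a chest infection is entered as fever, cough and dyspnea, three events appear in two other classes and none in the infection class. If it is entered as pneumonia, one event appears where a reader would look for it. Protocol 8.3 leaves sites to choose between these, and nothing later in the plan reconciles the two kinds of record.

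Safety is a stated objective alongside efficacy, and infection is an obvious question when two immunosuppressants are compared in children. At stake are the infection rows of Tables 65 and 66, the symptom rows, and the event totals in Tables 62 to 66.

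**Working it through.** The plan states no figure on this point, so the check is first one of text and then an illustration.

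**1. The two sentences side by side.**

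| Episode | First sentence, literal | Second sentence |
|---|---|---|
| Diagnosis known, typical signs only | Symptom list | Its condition is not met; its logic implies the diagnosis alone |
| Diagnosis known, plus an atypical sign | Symptom list | Diagnosis, plus the atypical sign |
| Diagnosis not known | Symptom list | Does not apply |

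Rows 1 and 2 show the conflict. Taken strictly as a rule and its exception, a typical pneumonia is entered as symptoms and an atypical one as pneumonia. Limiting the extra records to unusual signs makes sense only if the usual signs are already covered by the diagnosis.

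**2. Effect on each output if the first sentence is followed.**

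- Infection rows (Tables 65 and 66): lose the episode, both as an event and as a subject.
- Symptom rows and number of AEs: gain one entry per symptom.
- Subjects with any AE (Table 62): unchanged, because a child counts once however many entries there are.

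**3. Illustration of dilution.** The documents give no infection rates, so everything here except the sample size and the test level is assumed.

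- n = 135 per arm (Protocol 3.3.2; the safety set may differ).
- Two-sided 5% (Protocol 11.2.1).
- Assumed true incidence: p1 = 40%, p2 = 28%.
- s = assumed share of infected children who still carry an infection term, equal in both arms.

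Observed incidences are s·p1 and s·p2. The difference is s(p1 − p2), and the risk ratio is s·p1/(s·p2) = 40/28 = 1.43 for every s. With a = s·p1 and b = s·p2:

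SE = √{[a(1 − a) + b(1 − b)]/n}; power = Φ(d/SE − 1.96) + Φ(−d/SE − 1.96), where d = a − b.

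| s | Observed | d | SE | d/SE | Power |
|---|---|---|---|---|---|
| 1.00 | 40% vs 28% | 0.12 | 0.0572 | 2.10 | 55% |
| 0.75 | 30% vs 21% | 0.09 | 0.0528 | 1.71 | 40% |
| 0.50 | 20% vs 14% | 0.06 | 0.0456 | 1.32 | 26% |
| 0.25 | 10% vs 7% | 0.03 | 0.0339 | 0.89 | 14% |

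Using the pooled variance under the null gives the same rounded powers.

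**4. Other assumed rates** (15-point difference, same n, pooled variance under the null):

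| Assumed rates | s = 1.0 | s = 0.8 | s = 0.6 | s = 0.5 |
|---|---|---|---|---|
| 30% vs 15% | 84% | 73% | 58% | 50% |
| 40% vs 25% | 75% | 61% | 46% | 38% |
| 50% vs 35% | 70% | 55% | 40% | 32% |
| 60% vs 45% | 70% | 52% | 36% | 29% |

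The direction is the same throughout. If sites record the known diagnosis, s is close to 1 and no infection is lost from its row.

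**The case against.** A reader might infer that the protocol instructs sites not to record diagnoses, and that the infection comparison is therefore diluted. The documents do not support that. The first sentence is garbled and may be a translation slip. Its qualifier fits a diagnosis better than a symptom list, since symptoms can always be listed. The second sentence presupposes the diagnosis as the record. The preference for clinical over laboratory terms leans the same way, although it does not rank a diagnosis against symptoms. This part of the objection stands: the section contradicts itself and does not set a clear rule against diagnoses.

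It also stands that no infection endpoint or hypothesis is prespecified, and that Protocol 11.3.4 and SAP 8.1.4 make the analysis of adverse reactions descriptive. The trial was not sized for this comparison: under the 40% versus 28% assumption, power is only about 55% even with perfect recording. Equal misclassification leaves the risk ratio intact. A 2- to 4-fold inflation of events would merely restate an assumption of 2 to 4 recorded symptoms per infection.

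A further tempting reading is that Protocol 11.3.6 counts every significant laboratory change as a separate AE, on top of a symptom AE already reported. It can equally be read as a summary of the 8.3 rule, so double counting is possible but not prescribed.

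What the objection does not remove is that sites were given this wording, that a known diagnosis with only typical signs falls outside the exception's condition, and that Tables 65 and 66 carry P-values by class and term with no regrouping step.

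**Conclusion.** The point holds as a conflict of wording with a plausible effect on the safety tables. Sites that take the first sentence literally can move infections out of the infection class and split single episodes. The infection rows of Tables 65 and 66 can then be understated, and the symptom rows and event counts inflated. The overall subject-level AE incidence is not multiplied.

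The size is unknown. It depends on how many sites read the rule literally, and the documents do not say. The powers above rest wholly on assumed rates and shares and show a pattern only. With equal misclassification, the risk difference and power fall while the risk ratio stays the same. The trial is open-label and, by SAP 4.1, ran at 12 sites, so the wording could be applied differently by arm or site. Bias could then go in either direction.

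**What to change.** Replace the first sentence of the rule in Protocol 8.3, and match the eCRF guide, with: *Record the diagnosis as one AE when it is known or becomes known; record signs and symptoms separately only when there is no diagnosis or when they are not usually part of it.*

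In Protocol 11.3.6 and SAP 8.1.6, state that a laboratory change is counted as an AE only when it is not already supplementary information to a reported AE under 8.3.

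The SAP reports enrollment as complete, so a new sentence will not repair data already entered. Any grouping of symptom records into a diagnosed episode should follow a rule written beforehand and applied blind to arm. That step involves medical judgement and is more debatable than the wording change, which does not depend on it.

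The wording change costs one protocol sentence, the matching guidance and a clause on laboratory changes. The downside is that the reported number of AEs becomes smaller.
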